### **11.2.2 Primary Efficacy Analysis**

All patients entered are evaluable with respect to the efficacy endpoints. The primary endpoint is PFS. The benchmark median PFS for metastatic pancreatic adenocarcinoma who have progressed through first line chemotherapy is 3 months (Oettle, Riess et al. 2014).

The expected accrual rate is 18 patients per year and we add a 12-months maturation period after completing accrual. Patients enrolled during the continuous toxicity monitoring portion of the trial will all be included in the phase II efficacy analysis. All patients will be analyzed according to a strict intention-to-treat principle.

### **11.3 Determination of Sample Size**

The efficacy result will be summarized as a median PFS with a 1-sided 95% confidence interval. We will use a 1-sided test with a 5% significance level ( $\alpha$ ) to test the uni-directional hypothesis that the median PFS is prolonged from 3 to 4.5 months by combining RT combined with durvalumab in metastatic pancreas cancer patients who have progressed through first-line chemotherapy. With a statistical power ( $1-\beta$ ) of the study of 80%, we estimate an accrual time of 26 months for a total sample size of 39 patients. No early stopping rule for futility is planned due to the relatively rapid enrolment of patient in relation to the expected median PFS. The method used for sample size estimation assumes exponential survival distributions according to Dixon and Simon (Dixon et al. 1988)

### **11.4 Efficacy Endpoints**

#### **Primary**

Clinical Study Protocol  
Investigational Drug Substance: MEDI4736  
Study Number **ESR 15 11078**  
Edition Number **1.09**  
Date **01 Feb 2018**

**Progression free survival (PFS):** Progression free survival is defined as the time from the initiation of durvalumab to the first documented disease progression per RECIST 1.1 or death due to any cause, whichever occurs first. If a patient recurs and is eligible for retreatment, then only the time to the initial recurrence will be included in the evaluation of PFS. Patients who are alive with no evidence of disease at the time of last contact will be censored at that date.

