## **4. SUBJECT SELECTION**

### **4.1 Inclusion criteria**

For inclusion in the study subjects must fulfill all of the following criteria:

1. Written informed consent and any locally-required authorization (e.g., HIPAA in the USA, EU Data Privacy Directive in the EU) obtained from the subject prior to performing any protocol-related procedures, including screening evaluations
2. Age  $\geq$  18 years at time of study entry.
3. Eastern Cooperative Oncology Group (ECOG) performance status of 0 or 1.
4. Life expectancy of  $\geq$ 12 weeks as estimated by the investigator.
5. Biopsy-proven metastatic pancreatic adenocarcinoma with progression through standard first-line chemotherapy. Chemotherapy given as part of prior chemoradiation in the setting of non-metastatic pancreatic cancer does not count as a line of therapy.
6. At least 3 radiographically distinct pancreatic cancer lesions that are measurable by RECIST 1.1 criteria, including 2 that are (eligible) for RT
7. No lesion that would receive RT  $>$ 7 cm in greatest dimension.
8. Subjects must consent to all study procedures described in the protocol including radiographic evaluation and repeated blood draws.
9. Adequate normal organ and marrow function as defined below:
  - Hemoglobin  $\geq$  9.0 g/dL

- Absolute neutrophil count (ANC)  $\geq 1.5 \times 10^9/L$  ( $\geq 1500$  per  $\text{mm}^3$ )
- Platelet count  $\geq 100 \times 10^9/L$  ( $\geq 100,000$  per  $\text{mm}^3$ )
- Serum bilirubin  $\leq 1.5 \times$  institutional upper limit of normal (ULN). This will not apply to subjects with confirmed Gilbert's syndrome (persistent or recurrent hyperbilirubinemia that is predominantly unconjugated in the absence of hemolysis or hepatic pathology), who will be allowed only in consultation with their physician.
- AST (SGOT)/ALT (SGPT)  $\leq 2.5 \times$  institutional upper limit of normal unless liver metastases are present, in which case it must be  $\leq 5 \times$  ULN
- Serum creatinine  $\text{CL} > 40$  mL/min by the Cockcroft-Gault formula (Cockcroft and Gault 1976) or by 24-hour urine collection for determination of creatinine clearance:

Males:

$$\text{Creatinine CL (mL/min)} = \frac{\text{Weight (kg)} \times (140 - \text{Age})}{72 \times \text{serum creatinine (mg/dL)}}$$

Females:

$$\text{Creatinine CL (mL/min)} = \frac{\text{Weight (kg)} \times (140 - \text{Age})}{72 \times \text{serum creatinine (mg/dL)}} \times 0.85$$

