### **4.3 Withdrawal of Subjects from Study Treatment and/or Study**

#### **Permanent discontinuation of durvalumab**

An individual subject will not receive any further investigational product if any of the following occur in the subject in question:

1. Withdrawal of consent or lost to follow-up
2. Adverse event that, in the opinion of the investigator or the sponsor, contraindicates further dosing
3. Subject is determined to have met one or more of the exclusion criteria for study participation at study entry and continuing investigational therapy might constitute a safety risk
4. Pregnancy or intent to become pregnant
5. Any AE that meets criteria for discontinuation as defined in Section 6.6
6. Grade  $\geq 3$  infusion reaction
7. Subject noncompliance that, in the opinion of the investigator or sponsor, warrants withdrawal; e.g., refusal to adhere to scheduled visits
8. Initiation of alternative anticancer therapy including another investigational agent
9. Confirmation of PD and investigator determination that the subject is no longer benefiting from treatment with durvalumab

Subjects who are permanently discontinued from further receipt of investigational product, regardless of the reason (withdrawal of consent, due to an AE, other), will be identified as having permanently discontinued treatment.

Subjects who are permanently discontinued from receiving investigational product will be followed for safety per Section 10.3.1 and Appendix B or C, including the collection of any protocol-specified blood specimens, unless consent is withdrawn or the subject is lost to follow-up or enrolled in another clinical study. All subjects will be followed for survival. Subjects who decline to return to the site for evaluations will be offered follow-up by phone every month as an alternative.

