### **8.1.3 End of Treatment**

End of treatment is defined as the last planned dosing visit within the 12-month dosing period. For subjects who discontinue durvalumab prior to 12 months, end of treatment is considered the last visit where the decision is made to discontinue treatment. All required procedures may be completed within  $\pm 7$  days of the end of treatment visit. Repeat disease assessment is not required if performed within 28 days prior to the end of treatment visit.

Assessments for subjects who have completed durvalumab treatment and achieved disease control, or have discontinued durvalumab due to toxicity in the absence of confirmed progressive disease are provided in APPENDIX B.

Assessments for subjects who have discontinued durvalumab treatment due to confirmed PD are presented in APPENDIX C.

All subjects will be followed for survival until the end of the study regardless of further treatments, or until the sponsor ends the study.

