## **9. DISEASE EVALUATION AND METHODS**

### **9.1.1 Tumor Imaging**

Initial tumor imaging should be performed within 28 days prior to the start of durvalumab and every 8 weeks thereafter, or sooner if clinically indicated. A CT scan with IV and oral contrast of the chest, abdomen, and pelvis is required for initial tumor imaging and for all subsequent imaging. MRI scans are not permitted on this study.

The investigator must review baseline images to confirm the subject has measurable disease per RECIST 1.1. Subsequent images must also be reviewed for determination of treatment response. Subjects who have disease control following completion of 12 months of treatment or subjects who are withdrawn from durvalumab treatment for reasons other than confirmed PD will continue to have objective tumor assessments (see Appendix B).

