### **Secondary**

**Overall Response Rate (ORR):** The overall response rate is defined as the percentage of the patients who have a complete response (CR) or partial response (PR) as defined by RECIST 1.1. The patient's best overall response rate defined as the best response recorded from the start of the treatment until disease progression will be recorded.

**Clinical Benefit Rate (CBR) –** The clinical benefit rate is the percentage of patients that have achieved a complete response, partial response, or stable disease as defined by RECIST 1.1.

**Time to in-field progression –** The time to in-field progression is defined as the time from initiation of treatment to progression of disease within the radiation field.

**Overall Survival –** Overall survival is defined as the time from first treatment until death. Patients who are alive will be censored at the last date of patient contact.

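### PFS is censored at last contact instead of the last tumor scan, so time without scans counts as progression-free; the size depends on how many patients stop scans while still in contact

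*Combined protocol and SAP*

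**What the plan says.** - **Event.** Section 11.4 (Primary) runs PFS from the start of durvalumab to "first documented disease progression per RECIST 1.1 or death due to any cause, whichever occurs first".
- **Censoring.** The only PFS rule, in the same paragraph, is "Patients who are alive with no evidence of disease at the time of last contact will be censored at that date". Overall survival uses the same kind of date: "Patients who are alive will be censored at the last date of patient contact".
- **Scans.** Section 9.1.1 plans CT at baseline and "every 8 weeks thereafter, or sooner if clinically indicated". Sections 9.1.1 and 9.1.3 and Appendix B continue scans in patients who stop durvalumab without confirmed progression.
- **Contact.** Section 4.3, on patients who have permanently stopped durvalumab, says "Subjects who decline to return to the site for evaluations will be offered follow-up by phone every month as an alternative". Appendices B and C collect survival status by phone or email. Section 8.1.3 adds "All subjects will be followed for survival until the end of the study regardless of further treatments".
- **Population.** Section 11.2.2 says "All patients entered are evaluable with respect to the efficacy endpoints". Section 4.1 requires "At least 3 radiographically distinct pancreatic cancer lesions that are measurable by RECIST 1.1 criteria".

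No section gives the last scan as a PFS censoring date, or says what to do after missed scans.

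**The concern.** Last contact suits overall survival, because a call can establish that a patient is alive. It cannot establish RECIST 1.1 status. If a living patient without documented progression stops scans but is still reached by phone, the rule credits the time between last scan and last contact as progression-free, although progression could not have been seen in it. The primary test sets 39 patients against a fixed 3-month median. No concurrent arm shares the bias, and its direction favors treatment.

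The condition attached to the rule is a second, smaller defect. Patients with stable disease (SD) or partial response (PR) still have visible disease, so the condition literally describes only complete responders (CR).

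**Working it through.** **1. The plan's sample size (sections 11.2.2 and 11.3).** Inputs: medians 3 and 4.5 months, one-sided 5%, 80% power, exponential survival, 18 patients per year, 12 months of follow-up.
- Accrual: 39/18 × 12 = 26 months, as stated.
- Events: (1.645 + 0.842)² / [ln(3/4.5)]² = 37.6.
- P(event) = 1 − [exp(−12λ) − exp(−38λ)]/(26λ), with λ = ln 2/4.5, is 0.961.
- N = 37.6/0.961 = 39.1. The stated 39 reproduces.

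**2. Patients affected under full scanning.** P(event) is 0.990 at a median of 3 months and 0.961 at 4.5. The expected number alive and progression-free at cutoff is therefore 0.4 or 1.5 of 39. With so few, the two rules nearly coincide.

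**3. Assumptions for scan drop-out.** Section 11.3 names no test, and the documents give no drop-out rate. Assumed:
- true median PFS 3 months, with progression dated exactly (the effect of dating it at 8-weekly scans is a separate matter, left out here);
- median survival after progression 3 months, guided by 5.9 − 2.9 in the oxaliplatin arm of the cited second-line trial (section 1.1);
- 10, 20 or 30% of patients progression-free at week 8 stop scans then, independently of progression;
- a death during contact is an event under both rules.

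Week 8 is 1.84 months, so exp(−1.84 × ln 2/3) = 0.65, or about 25.5 of 39, are progression-free then. Drop-outs number about 2.6/5.1/7.6 per trial.

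**4. Tests.** Exponential: 2 × (total time) × ln 2/3 against chi-square with twice the number of events as degrees of freedom. Kaplan-Meier: log-log lower bound for PFS at 3 months above 0.5. Without drop-out and with last-contact censoring, error is 5.1% and 5.3%. There were 200,000 simulated trials per setting, except 40,000 for the two-missed-scan rule.

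**5. One-sided error (%) at 10/20/30% drop-out**

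| Scenario | Test | Last contact | Last scan |
|---|---|---|---|
| Full scanning, no drop-out | Exponential | 5.1 | 4.8 |
| Contact to death or cutoff (as planned) | Exponential | 11.6/21.1/32.8 | 9.4/15.5/23.3 |
| Contact to death or cutoff (as planned) | Kaplan-Meier | 7.5/10.3/13.6 | 6.8/8.6/10.9 |
| Contact lost 3 months after last scan | Exponential | 7.7/11.6/16.8 | 4.7/4.2/3.9 |
| Contact lost 3 months after last scan | Kaplan-Meier | 7.5/10.2/13.4 | 3.9/4.1/4.3 |
| Drop-outs are those progressing in weeks 8–16; contact lost at 3 months | Exponential | 10.9/20.8/34.5 | 8.0/12.1/17.7 |

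**6. Splitting the planned case.** The excess over 5.1% under last contact is 6.5/16.0/27.7 points. Moving to the last scan removes 11.6 − 9.4 = 2.2, 21.1 − 15.5 = 5.6 and 32.8 − 23.3 = 9.5 points, about a third. The rest comes from deaths long after scans stopped, which are events under both rules. Only about 0.2 to 0.5 patients per trial are alive and censored differently, but each can add many months to total time, because cutoff falls 12 to 38 months after entry. With Kaplan-Meier the rule removes 0.7/1.7/2.7 points. Censoring progression or death after two or more consecutive missed scans at the last scan before the gap gives 4.3/4.2/3.6%.

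**7. The 3-month case.** Events are the same under both rules (36.5/34.4/32.2); last contact only adds 6.5/13.0/19.4 unscanned patient-months. As a check at 20%, 13.0/3 is about 4.3 living drop-outs, in line with 39 − 34.4 = 4.6 censored patients, of whom about 0.4 are censored at cutoff. Varying the post-progression median from 1.5 to 4.5 months gives 6.9–8.2/9.5–12.6/12.7–18.8% against 4.4–4.9/3.8–4.5/3.2–4.3%.

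**The case against.** **The trigger is a departure from the plan.** Scans are scheduled until progression, on and off drug. Withdrawal of consent ends observation (section 4.3), and patients who stopped for confirmed progression already have their event. No document supports a 10 to 30% drop-out. This stands: the percentages are scenarios, and the effect nearly vanishes under full scanning.

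**The sentence can be read another way.** A call cannot show absence of disease, so contact with a disease assessment may be meant. Read literally, the rule covers only complete responders and does not censor SD or PR patients at last contact at all. This stands in part: the error figures need the looser reading, that every unprogressed patient is censored at last contact. But the literal reading leaves most unprogressed patients with no censoring date, so the sentence needs replacing either way.

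**The benchmark's rule is unknown.** The documents do not give the censoring rule or scan schedule behind the 3-month figure, so the net bias of the historical comparison cannot be established. This stands. The direction within this arm is not in doubt.

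**The remedy is partial.** It is: late deaths and informative drop-out still inflate error.

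Three stronger readings are tempting but unsupported:
- That SD and PR patients fall out of the analysis. Section 11.2.2 keeps every patient evaluable, and section 11.4 makes only progression or death an event, so censoring is the consistent treatment.
- That the contrast of 7.7/11.6/16.8% with 4.7/4.2/3.9% describes the trial as planned. It needs contact to be lost 3 months after the last scan, whereas section 8.1.3 plans survival follow-up to study end.
- That death after missed scans has no rule. Section 11.4 counts it as an event.

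**Conclusion.** The concern holds as a wrong censoring date for PFS and a wording defect in the condition attached to it. For living, unprogressed patients whose scans stop while contact continues, unscanned time counts as progression-free, which biases the comparison with 3 months toward treatment.

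The size rests on assumed scan drop-out, exponential PFS and the choice of test. In the case closest to the plan, contact to death or cutoff, the censoring date accounts for 2.2/5.6/9.5 points of one-sided error at 10/20/30% drop-out with the exponential test, and 0.7/1.7/2.7 points with Kaplan-Meier. A reader might attribute the whole rise to 11.6/21.1/32.8% to the censoring date, but about two thirds of the excess comes from late deaths. With full scanning the difference is 0.3 points. The sentence should be corrected before analysis; the finding does not show that the trial's error rate is in fact inflated.

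**What to change.** Replace the censoring sentence in section 11.4 (Primary) with: *Patients alive without documented RECIST 1.1 progression (CR, PR or SD) are censored at the date of their last evaluable tumor assessment, or at Day 1 if there is none.* Keep death from any cause as an event in the primary analysis, and keep last contact as the censoring date for overall survival only.

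Add a sensitivity analysis that censors progression or death after two or more consecutive missed scans at the last evaluable scan before the gap. This is the rule that addresses late deaths. Like last-scan censoring, it assumes that stopping scans is unrelated to progression.

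Cost: one sentence and one extra analysis. Scan dates are already collected, no procedure changes and N stays 39. The downside is less follow-up time. At a true median of 4.5 months with contact lost at 3 months, power is 78/75/71% at 10/20/30% drop-out, against 82% with full scanning. Last-contact censoring shows 84/87/89%, but the unscanned time raises those figures. Without drop-out, power is 81% under last scan against 82% under last contact. Living patients with no post-baseline scan contribute no time; section 4.4 allows some of them to be replaced.

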### **Secondary**

**Overall Response Rate (ORR):** The overall response rate is defined as the percentage of the patients who have a complete response (CR) or partial response (PR) as defined by RECIST 1.1. The patient's best overall response rate defined as the best response recorded from the start of the treatment until disease progression will be recorded.

**Clinical Benefit Rate (CBR) –** The clinical benefit rate is the percentage of patients that have achieved a complete response, partial response, or stable disease as defined by RECIST 1.1.

**Time to in-field progression –** The time to in-field progression is defined as the time from initiation of treatment to progression of disease within the radiation field.

**Overall Survival –** Overall survival is defined as the time from first treatment until death. Patients who are alive will be censored at the last date of patient contact.

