- In addition, subjects may continue to receive durvalumab beyond confirmed PD in the absence of clinically significant deterioration and if investigators consider that subjects continue to receive benefit from treatment.

Modification of RECIST as described may discourage the early discontinuation of durvalumab and provide a more complete evaluation of its anti-tumor activity than would be seen with conventional response criteria. Nonetheless, the efficacy analysis will be conducted by programmatically deriving each efficacy endpoint based on RECIST 1.1 criteria.

Of note, clinically significant deterioration is considered to be a rapid tumor progression that necessitates treatment with anti-cancer therapy other than durvalumab or with symptomatic progression that requires urgent medical intervention (e.g., central nervous system metastasis, respiratory failure due to tumor compression, spinal cord compression).

Subjects who have disease control following completion of 12 months of treatment or subjects who are withdrawn from durvalumab treatment for reasons other than confirmed PD will continue to have objective tumor assessments (see Appendix B).

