## APPENDIX B

### Schedule of study procedures: follow-up for subjects who have completed durvalumab treatment and achieved disease control (until confirmed progression of disease) and subjects who have discontinued durvalumab due to toxicity in the absence of confirmed progression of disease

Evaluation	Time Since Last Dose of durvalumab							
	Day ( $\pm 3$ )	Months ( $\pm 1$ week)						12 Months and Every 6 Months ( $\pm 2$ weeks)
	30	2	3	4	6	8	10	
Physical examination a	X							
Vital signs (temperature, respiratory rate, blood pressure, pulse)	X							
Weight	X							
AE/SAE assessment	X	X	X					
Concomitant medications	X	X	X					
ECOG performance status	X	X	X					
Subsequent anti-cancer therapy	X	X	X	X	X	X	X	X
Survival status (phone call or email)	X	X	X	X	X	X	X	X (every 2 months)
Hematology	X	X	X					
Serum chemistry	X	X	X					
Thyroid function tests (TSH, and fT3 and fT4) b	X							
CA 19-9	X							
Blood for correlative studies	X							
Blood for Future Biomedical Research	X							
Patient questionnaire (patient reported outcomes) c and health resource use	X		X					
Tumor assessment (CT)	Every 2 months							

Clinical Study Protocol

Investigational Drug Substance: MEDI4736

Study Number **ESR 15 11078**

[figure not shown]
Edition Number **1.09**

Date **01 Feb 2018**

- a Full physical exam
- b Free T3 and free T4 will only be measured if TSH is abnormal. They should also be measured if there is clinical suspicion of an adverse event related to the endocrine system.
- c For patient questionnaires different approaches based on indication and study design

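### Best response and clinical benefit are not cut off at new anticancer therapy, so a response first reached on next-line treatment would count for durvalumab plus RT

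*Combined protocol and SAP*

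**What the plan says.** - **Leaving durvalumab.** Section 4.3, item 8, lists "Initiation of alternative anticancer therapy including another investigational agent" among the reasons for permanent discontinuation. That reason is not confirmed progression.
- **Scanning afterwards.** Section 9.1.1 says that "subjects who are withdrawn from durvalumab treatment for reasons other than confirmed PD will continue to have objective tumor assessments", and Section 9.1.3 repeats it. Appendix B sets CT every 2 months, and the same table has a row for "Subsequent anti-cancer therapy".
- **Response endpoints.** Section 11.4 defines best response as the "best response recorded from the start of the treatment until disease progression", and Section 9.1.4 uses the same window. CBR counts complete response, partial response or stable disease, with no window. Responses need a confirmatory scan (Section 9.1.3 and the imaging footnote to the schedule of assessments).
- **PFS.** Section 11.4 runs PFS "to the first documented disease progression per RECIST 1.1 or death due to any cause, whichever occurs first". The only censoring rule concerns last contact.
- **Derivation and population.** Section 9.1.3 derives every efficacy endpoint programmatically from standard RECIST 1.1. Section 11.2.2 applies strict intention to treat.

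No efficacy definition mentions new therapy. Other parts of the protocol do: the SAE reporting period can end there (Section 10.3.2), and durvalumab retreatment requires that no other treatment was given for the progression or recurrence (Section 6.2).

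**The concern.** Read together, these sections leave a route by which the effect of another treatment is scored as an effect of the study regimen. A patient stops durvalumab for toxicity, say, with no RECIST progression. Chemotherapy is started, the two-monthly CT scans continue, and a partial response appears and is confirmed. Progression has not occurred, so the best-response window is still open, and a program that follows Section 11.4 records a responder to durvalumab plus RT.

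This matters because the trial has one arm and its benchmark is historical second-line chemotherapy (Section 2.1.1). Eligible patients have had only one line for metastatic disease, so second-line chemotherapy is a natural next step, although Section 1.1 says there is no accepted standard. No concurrent arm exists in which such responses would balance out.

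**Working it through.** **Which patients are affected**

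- Leaves at or after a first RECIST 1.1 progression, confirmed or not: under Sections 9.1.3 and 11.4 that first progression already ends PFS and the best-response window. Not affected.
- Leaves without RECIST 1.1 progression and takes no new therapy: every scan reflects the study regimen. Not affected.
- Leaves without RECIST 1.1 progression, starts new systemic therapy and keeps being scanned: affected.

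**ORR**

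The denominator is 39 (Section 11.3). One response reached only on later therapy adds 1/39 = 2.6 points. The expected addition is switchers × response rate on next-line therapy / 39. Neither input is in the documents, so these are assumed ranges:

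- 2 switchers, 5% responding: 2 × 0.05 = 0.1 responder; 0.1/39 = 0.3 points. Chance of at least one: 1 − 0.95² = 10%.
- 4 switchers, 10%: 0.4 responder; 1.0 point. Chance: 1 − 0.90⁴ = 34%.
- 8 switchers, 20%: 1.6 responders; 4.1 points. Chance: 1 − 0.80⁸ = 83%.

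The sign is fixed, because a later scan can raise a best response but cannot lower it.

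**CBR**

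A patient with one progression-free scan before switching normally already qualifies through stable disease. The gain is confined to patients who switch before their first on-study scan at week 8, and some of those may be replaced (Sections 4.4 and 6.1.1).

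**PFS**

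The plan's own figure first. Events = (1.645 + 0.842)² / ln(1.5)² = 6.18 / 0.164 = 37.6. At a 4.5-month median, with 26 months of uniform accrual and 12 more of follow-up, the event probability is 0.961. N = 37.6 / 0.961 = 39.1, and 39 at 18 per year takes 26.0 months. The sample size reproduces, and this point does not change it.

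The same exponential model was then simulated with 40,000 trials per setting, n = 39 and a true median of 3 months, rejecting if ln(estimated median/3) × √events > 1.645. With no switching it rejects in 3.8 to 3.9% of trials. Simulation error is about √(0.037 × 0.963 / 40,000) = 0.1 point. The post-switch medians of 2.0 and 2.9 months are the two arms quoted in Section 1.1; the switching fractions are assumed.

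1. *Switch at month 2 while progression-free* (as after toxicity), so that chemotherapy time replaces study time. With 5 / 10 / 20% selected to switch, rejection is 3.7 / 3.7 / 3.6% at a 2.9-month median and 3.3 / 2.7 / 2.0% at 2.0 months. There is no inflation.
2. *Switch at the moment of progression that is never recorded*, so that chemotherapy time is added to a full PFS time. With 5 / 10 / 20% switching, rejection is 5.9 / 8.7 / 16.7% (2.0 months) and 7.1 / 12.2 / 26.6% (2.9 months). At 20%, the apparent median is about 3 + 0.2 × 2.0 = 3.4 to 3 + 0.2 × 2.9 = 3.6 months.
3. *As in 1, but with a 4.5-month median on chemotherapy*, better than the benchmark. With 10 / 20 / 40% selected, rejection is about 6 / 9 / 17%.

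The direction for PFS therefore depends on why patients switch and on how well the next therapy works.

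**The case against.** Four points count against this.

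- **Scoring after new therapy is never stated.** It follows only from definitions that stop at progression, death or last contact. Appendix B's title also names only treatment completers with disease control and toxicity discontinuations. That is true, but Section 9.1.1 covers every reason other than confirmed progression, and toxicity leavers alone are enough to open the route.
- **Confirmation limits the effect.** A single good scan on chemotherapy should not count, since a confirmatory scan is required. This stands and keeps the numbers small.
- **PFS regardless of later therapy is what strict intention to treat implies.** This stands. It does not carry over to ORR and CBR: intention to treat fixes who is analysed, not which treatment a response belongs to.
- **The deterioration route is partly covered.** Section 9.1.3 describes "rapid tumor progression that necessitates treatment with anti-cancer therapy other than durvalumab", and Section 11.4 does not count that as progression by itself. A reader might infer that such patients routinely escape a PFS event. But Section 9.1.1 allows earlier imaging when clinically indicated, and Sections 8.1.3 and 13.2 imply a disease assessment around the end of treatment, where progression would normally be recorded.

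A reader might also infer that PFS is inflated in one favourable direction. The documents do not support that: with the chemotherapy medians they quote, switching while progression-free leaves the error rate unchanged or lowers it.

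**Conclusion.** The gap is real for ORR and, to a smaller degree, CBR. As written, a confirmed response first reached on next-line therapy counts for durvalumab plus RT in any patient who left without RECIST 1.1 progression. It can only raise ORR: by 2.6 points per patient, and by about 0.3 to 4 points in expectation under assumed switching and response rates. These are secondary endpoints with no stated hypothesis test, so the trial's formal conclusion does not rest on them.

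For PFS the finding is limited. One-sided type I error is about 2 to 4% if patients switch while progression-free to chemotherapy with a 2.0 to 2.9 month median. It reaches about 6 to 27% only if 5 to 20% switch at the point of otherwise unrecorded progression. The documents give no basis for assuming the second case, and the primary definition is defensible as it stands.

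It would also be too wide to say that everyone leaving without *confirmed* progression is affected, because a first unconfirmed RECIST 1.1 progression already closes both endpoints. This is a cheap improvement, not a flaw in the design.

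**What to change.** 1. In Sections 9.1.4 and 11.4, state that only tumor assessments made before the first non-protocol systemic anticancer therapy count toward best response, ORR and CBR. A confirmatory scan taken after that date would then not count either; the text should say so.
2. Report how many patients started such therapy before RECIST 1.1 progression.
3. Keep the intention-to-treat PFS definition as primary. Optionally prespecify a sensitivity analysis in two versions: new therapy before RECIST 1.1 progression as an event on its start date, and censoring at the last scan before it. Show both, because the event version is severe when switches are not due to progression. With a true median of 4.5 months, switches at month 2 and a 3.0-month median on chemotherapy, selecting 10 / 20 / 40% of patients to leave gives power of about 62 / 43 / 11% with the event version and 76 / 73 / 66% with censoring, against about 78% with no switching.

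The cost is two sentences, a count and, if wanted, one supportive analysis. Appendix B already collects subsequent therapy; check that the form captures its start date. Sample size, scanning and patient management do not change. ORR and CBR may come out slightly less favorable.
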